7.2. Analysis up to Visit 8 (Day 420)

The final analyses will be descriptive and will be presented by study group, with pooled data from the two steps for the placebo groups.

7.2.1. Analysis of demographics

Withdrawal status will be summarised by group using descriptive statistics:

The number of subjects enrolled into the study as well as the number of subjects excluded from ATP analyses will be tabulated.

The numbers of withdrawn subjects will be tabulated according to the reason for withdrawal.

7.2.2. Analysis of safety

The primary analysis will be performed on the TVC and, if in any vaccine group and at any time point the percentage of vaccinated subjects excluded from the ATP cohort is at least 10%, a second analysis will be performed on the ATP cohort to complement the TVC.

Study alias & e-track number(s): NTHI MCAT-001 (201281)

The percentage of subjects with at least one **local AE** (solicited and unsolicited), with at least one **general AE** (solicited and unsolicited) and with any AE during the 7-day or 30-day follow-up period will be tabulated after Dose 1 and Dose 2 and overall with exact 95% CI. The same computations will be done for Grade 3 AEs, any AEs causally related to vaccination and any Grade 3 AEs causally related to vaccination.

The percentage of subjects/doses reporting each individual solicited local (any grade, Grade 3) and general (any grade, Grade 3, any causally related to vaccination and any Grade 3 causally related to vaccination) AE during the 7-days (Day 0 to Day 6) follow-up period will be tabulated for each group as follows:

- Overall, the percentage of subjects with the symptom and its exact 95% CI
- Overall, the percentage of doses with the symptom and its exact 95% CI
- At each study dose (visit), the percentage of subjects with the symptom and its exact 95% CI.

The exact 95% CIs will be calculated assuming independence between doses. For fever, additional analyses will be performed by 0.5°C increments.

The verbatim reports of **unsolicited symptoms** will be reviewed by a physician and the signs and symptoms will be coded according to the MedDRA Dictionary for Adverse Reaction Terminology. Every verbatim term will be matched with the appropriate preferred term (PT). The percentage of subjects with unsolicited symptoms within 30 days after any doses with its exact 95% CI will be tabulated by group and by MedDRA PT. Similar tabulation will be done for Grade 3 unsolicited symptoms, for unsolicited symptoms that resulted in a medically attended visit, for unsolicited symptoms causally related to vaccination and for Grade 3 symptoms causally related to the vaccination.

For each group and for each **haematology and biochemistry parameter**:

- The percentage of subjects having haematology and biochemistry results below or above the normal laboratory ranges will be tabulated by time point.
- The maximum grading from Screening up to Visit 8 (Day 420) will be tabulated (grades will be based on local laboratory normal ranges and derived from FDA Guidance to Industry “Toxicity Grading Scale for Healthy Adult and Adolescent Volunteers Enrolled in Preventive Vaccine Clinical Trials”. Those laboratory parameters not included in the FDA grading scale will not be graded).

The number of subjects who experienced at least one SAE or any pIMDs from first vaccination up to study conclusion will be reported.

The percentage of subjects/dose using **concomitant medication/ product** (any medication/ product, any antipyretic and any antipyretic taken prophylactically,

Study alias & e-track number(s): NTHI MCAT-001 (201281)

respectively) during the 30-day follow-up period (Day 0 – Day 29) will be summarised per group for each dose and overall per dose.

The number of subjects who experienced any AE leading to study withdrawal, or any SAE related to study participation or concurrent GSK medication/ vaccination, from first vaccination up to study conclusion will be reported.

Pregnancy reports from first vaccination up to study conclusion and pregnancy outcomes will be described in detail.

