(b) Treatment number allocation with randomisation at Visit 1 (Day 0); treatment number allocation without randomisation at Visit 4 (Day 60).

(c) Only for subjects belonging to the CMI sub-cohort.

(d) Distribution of 2 Diary Cards after each vaccination:

- a 1st one distributed on the day of vaccination for recording of solicited and unsolicited AEs and concomitant medications/ products and vaccinations from Day 0 to Day 6 after each vaccination.
- a 2nd one distributed on the 7 day post-vaccination visit for recording of unsolicited AEs and concomitant medications/ products and vaccinations from Day 7 to Day 29 after each vaccination.

(e) Screening evaluations may be completed 1 to 28 days before Day 0. Site staff should allow sufficient time between the Screening and Visit 1 to receive and review screening safety laboratory test results. If a delay occurs such that the interval between Screening and the Visit 1 vaccination exceeds 28 days, a re-screening visit should be scheduled before Visit 1 during which blood sample collection for safety laboratory assessment must be repeated; an interim medical history and physical examination must be obtained and inclusion / exclusion criteria must be re-reviewed.

(f) Complete physical examination including vital signs.

(g) From Screening to Visit 1, only those SAEs that are considered related to study participation or to concomitant use of GSK products or any fatal events need to be recorded. GSK products or any fatal event need to be recorded.

(h) Concomitant medication products/vaccination as indicated in Section 6.6.1 need to be recorded.

(i) *This test should be repeated on another day if the first attempt doesn't meet quality requirements as described by ATS/ERS standards (Miller, 2005).*

Table 7 Intervals between study visits

| Interval | Optimal length of interval ^(a) | Allowed interval |
|---|---|----------------------------|
| Screening (Pre-Day 0) → Visit 1 (Day 0) | 5 days | 1 – 28 days ^(b) |
| Visit 1 (Day 0) → Visit 2 (Day 7) | 7 days | 7 - 9 days |
| Visit 1 (Day 0) → Visit 3 (Day 30) | 30 days | 30 - 40 days |
| Visit 1 (Day 0) → Visit 4 (Day 60) | 60 days | 60 - 70 days |
| Visit 4 (Day 60) → Visit 5 (Day 67) | 7 days | 7 - 9 days |
| Visit 4 (Day 60) → Visit 6 (Day 90) | 30 days | 30 - 40 days |
| Visit 1 (Day 0) → Visit 7 (Day 210) | 210 days | 210 - 230 days |
| Visit 1 (Day 0) → Visit 8 (Day 420) | 420 days | 420 - 440 days |

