8.3. Detecting and recording adverse events, serious adverse events and pregnancies

8.3.1. Time period for detecting and recording adverse events, serious adverse events and pregnancies

All AEs starting within 30 days following administration of each dose/ of study vaccines (Day 0 to Day 30) must be recorded into the appropriate section of the eCRF, irrespective of intensity or whether or not they are considered vaccination-related.

The time period for collecting and recording SAEs will begin at the first receipt of study vaccines and will end at study conclusion. See Section 8.4 for instructions on reporting of SAEs.

All AEs/SAEs leading to withdrawal from the study will be collected and recorded from the time of the first receipt of study vaccines until study conclusion.

In addition to the above-mentioned reporting requirements and in order to fulfil international reporting obligations, SAEs that are related to study participation (i.e. protocol-mandated procedures, invasive tests, a change from existing therapy) or are related to a concurrent GSK medication/vaccine will be collected and recorded from the time the subject consents to participate in the study until she/he is discharged from the study.

The time period for collecting and recording of pIMDs will begin at the first receipt of study vaccine and will end at study conclusion. See Section 8.4 for instructions on reporting of pIMDs.

The time period for collecting and recording pregnancies will begin at the first receipt of study vaccine and will end at study conclusion. See Section 8.4 for instructions on reporting of pregnancies.

The time period for collecting and recording of intercurrent medical conditions requiring medical attention will begin at the first receipt of study vaccine and will end at study conclusion.

Table 19 Reporting periods for collecting safety information

| Event | Screening Visit* | Visit 1 | 7 d post | 30 d post | Visit 4 | 7 d post | 30 d post | Study Conclusion |
|--|------------------|---------|----------|-----------|---------|----------|-----------|------------------|
| | | Dose 1 | Dose 1 | Dose 1 | Dose 2 | Dose 2 | Dose 2 | |
| | | Day 0 | Day 6 | Day 29 | Day 60 | Day 66 | Day 89 | Day 210 |
| Solicited local and general AEs | | | | | | | | |
| Unsolicited AEs | | | | | | | | |
| AEs/SAEs leading to withdrawal from the study | | | | | | | | |
| SAEs | | | | | | | | |

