- The maximum grading from Screening up to Visit 8 (Day 420) will be tabulated (grades will be based on local laboratory normal ranges and derived from FDA Guidance to Industry “Toxicity Grading Scale for Healthy Adult and Adolescent Volunteers Enrolled in Preventive Vaccine Clinical Trials”, see [APPENDIX C](#). Those laboratory parameters not included in the FDA grading scale will not be graded).

The number of subjects who experienced at least one **SAE** or any **pIMDs** during the entire study period will be reported.

The percentage of subjects/dose using **concomitant medication/ product** (any medication/ product, any antipyretic and any antipyretic taken prophylactically, respectively) during the 30-day follow-up period (Day 0 – Day 29) will be summarised per group for each dose and overall per dose.

The number of subjects who experienced any **AE leading to study withdrawal**, from first vaccination up to study conclusion, or any **SAE related to study participation of concurrent GSK medication/ vaccination**, during the entire study period, will be reported.

iSRC safety evaluations

At each iSRC time point, a blinded review will be done by the GSK SRT followed by an unblinded review of safety data by the iSRC (refer to Section 8.10 for more information). No individual clinical study report (CSR) will be written as a result of these safety evaluations.

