- The maximum grading from Screening up to Visit 6 (Day 90) will be tabulated (grades will be based on local laboratory normal ranges and derived from FDA Guidance to Industry “Toxicity Grading Scale for Healthy Adult and Adolescent Volunteers Enrolled in Preventive Vaccine Clinical Trials”. Those laboratory parameters not included in the FDA grading scale will not be graded).

The number of subjects who experienced at least one SAE or any pIMDs from first vaccination up to 30 days post-Dose 2 will be reported.

The percentage of subjects/dose using **concomitant medication/ product** (any medication/ product, any antipyretic and any antipyretic taken prophylactically, respectively) during the 30-day follow-up period (Day 0 – Day 29) will be summarised per group for each dose and overall per dose.

The number of subjects who experienced any **AE leading to study withdrawal, or any SAE related to study participation or concurrent GSK medication/ vaccination**, from first vaccination up to 30 days post-Dose 2 will be reported.

Pregnancy reports from first vaccination up to 30 days post-Dose 2 and pregnancy outcomes will be described in detail.

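### The SAP counts SAEs related to study participation or a concurrent GSK product only from first vaccination, although the protocol collects them from consent and reports them over the entire study period

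*SAP*

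**What the plan says.** Protocol 8.3.1 sets two start points for SAE collection. For SAEs in general: "The time period for collecting and recording SAEs will begin at the first receipt of study vaccines and will end at study conclusion". SAEs related to study participation (protocol-mandated procedures, invasive tests, a change from existing therapy) or to a concurrent GSK product are added to that, and these "will be collected and recorded from the time the subject consents to participate in the study until she/he is discharged from the study". The footnotes to the procedure tables in protocol 5.5 agree for both steps. They limit what is recorded before vaccination to this class and fatal events: "From Screening to Visit 1, only those SAEs that are considered related to study participation or to concomitant use of GSK products".

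Protocol 10.6.2 then plans the reporting. One sentence gives AEs leading to withdrawal the window "from first vaccination up to study conclusion, or any" and goes straight on to SAEs related to participation or a GSK product, which it assigns to the entire study period.

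SAP Amendment 2 merges the two items. For the final analysis, section 7.2.2 has a single window at the end of the sentence: "any SAE related to study participation or concurrent GSK medication/ vaccination, from first vaccination up to study conclusion will be reported". For the Day 90 analysis, section 7.1.2 does the same: "from first vaccination up to 30 days post-Dose 2 will be reported". SAP section 10, on changes from planned analyses, records none.

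**The concern.** This class of SAE is the only one, apart from deaths, that the protocol records before vaccination. When the SAP starts the count at first vaccination, it removes the part of the collection period that sets this class apart. A serious event caused by a screening procedure in a subject who was later vaccinated would be in the database but not in the number that the protocol says will be reported. The report would also give no sign that the window had been narrowed, because the SAP declares no departure. Protocol 10.8 asks for changes from its plan to be described and justified in the final report, and a change that nobody has noticed is unlikely to be.

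**Working it through.** The main check is a comparison of texts. The documents give no SAE rate, so an expected number of omitted events cannot be calculated.

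**Step 1. Where each window starts.**

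| Item | Collected from (protocol 8.3.1) | Reported over (protocol 10.6.2) | Counted from (SAP 7.1.2, 7.2.2) |
|---|---|---|---|
| AEs leading to withdrawal | First vaccination | First vaccination to study conclusion | First vaccination |
| SAEs in general, pIMDs | First vaccination | Entire study period | First vaccination |
| SAEs related to participation or a GSK product | Consent | Entire study period | First vaccination |

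In the first two rows the SAP starts where collection starts, so nothing collected is lost. Only in the third row does the SAP start later than collection.

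**Step 2. Whether the entire study period includes screening.** Protocol 3.1 runs the study for each subject from screening to study end and begins Epoch 001 at the Screening Visit. It therefore does.

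**Step 3. Whether document versions or SAP convention explain the difference.** The SAP history cites protocol Amendment 1. The changes shown in protocol Appendix D do not touch 10.6.2, so the version does not explain it. Starting at first vaccination is not a general SAP rule either: the maximum laboratory grading in 7.1.2 and 7.2.2 runs from Screening.

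**Step 4. How much time is left out.** Protocol Table 7 allows 1 to 28 days from Screening to Visit 1, with 5 days optimal. The share of a subject's time to Day 420 is s / (s + 420), where s is the number of screening days:

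- s = 1: 1/421 = 0.2%
- s = 5: 5/425 = 1.2%
- s = 28: 28/448 = 6.3%

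These figures take consent to be given at the Screening Visit and assume no re-screening. Re-screening, which protocol 5.5 provides for, could lengthen the interval.

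**Step 5. What happens in that time.** The safety blood sample at Screening is taken in both steps. Spirometry is done in Step 2 only, at Screening and at Visit 8, with post-bronchodilator testing if the first result meets the criteria in protocol 5.6.8. The Visit 8 spirometry lies inside the final reporting window, so the screening test is the scheduled one that falls outside.

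**The case against.** The best defence is that the protocol uses its phrase loosely. Protocol 10.6.2 also says that SAEs and pIMDs in general "during the entire study period will be reported", although their collection begins at first vaccination. The SAP tightened the wording there correctly and may simply have applied the same edit to the next item. That is a plausible account of how the mismatch arose, but it does not remove it. For this class, the same protocol sentence sets the entire study period against a start at first vaccination, and 8.3.1 fixes the start at consent.

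Several objections limit the weight of the point, and they stand:

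- Protocol 8.3.1 gives international reporting obligations as its reason for collecting from consent. SAEs go to the sponsor within 24 hours (protocol 8.4.1) whatever is tabulated later. A reader might infer a failure of safety oversight, and the documents do not support that.
- The SAE endpoint runs from first vaccination in both documents and is unchanged.
- A reader might take the Day 90 share, 28/(28 + 90) = 23.7%, as the size of the problem. It is a share of calendar time, not of events. It assumes the longest allowed screening interval (5/95 = 5.3% at the optimal one). It also concerns an analysis that SAP 9.1 labels internal and re-produces on cleaned data at the end.
- A reader might also infer that the SAP breaks the protocol by not counting screening failures. Both documents base the primary safety analysis on the TVC, which holds vaccinated subjects only. Protocol 9.3 collects these SAEs for screening failures, but neither document plans to tabulate them.
- Table and listing formats are in a separate annex that is not available here, and individual listings are due at the final analysis. The SAP text shows omission from the stated count. It does not show that the event would be absent from the study report.

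**Conclusion.** The two documents conflict, and the SAP is wrong as written on this item: followed literally, it leaves a collected pre-vaccination event out of a count that the protocol specifies. The interval concerned is at most about 6% of the time to Day 420 and about 1% at the optimal screening interval.

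In practice the effect is probably small. Related serious events during screening are likely to be rare, and there may be none. Eligibility is checked again at Visit 1, so a subject with such an event may never be vaccinated, and correcting the window within the TVC may then recover few or no events. For the same reason, a claim that procedure-related harm would be understated by a definite amount cannot be supported.

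The conclusion rests on reading the entire study period as starting at screening, which protocol 3.1 and 8.3.1 support. It is a defect of completeness and of consistency between protocol and SAP. It should be corrected because correction is easy, not because any conclusion of the trial depends on it.

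**What to change.** In SAP 7.1.2 and 7.2.2, split the sentence in two:

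1. Keep AEs leading to study withdrawal from first vaccination, as now.
2. Report SAEs related to study participation or a concurrent GSK product from informed consent to the analysis cut-off (30 days post-Dose 2 in 7.1.2, study conclusion in 7.2.2). Put events before first vaccination on a separate line, so that they are not read as following vaccine exposure.

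Optionally, list descriptively, outside the vaccine groups, the SAEs that protocol 9.3 collects for screening failures. This goes beyond what either document currently plans to report.

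If the sponsor prefers the narrower window, SAP section 10 should declare and justify it.

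The cost is a wording change in two sections and one extra table line. The data are already collected, and no other analysis changes.

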7.2.3. Analysis of immunogenicity

The primary analysis will be performed on the ATP cohort for immunogenicity and if, in any study group, the percentage of vaccinated subjects with serological results excluded from the ATP cohort is at least 10%, a second analysis will be performed on the TVC.

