6.1.2.1. According-to-protocol cohort for analysis of immunogenicity (Epoch 001)

The ATP cohort for immunogenicity will include all subjects in the TVC:

- Who met all eligibility criteria.
- For whom the administration route and site of the vaccines was according to protocol.
- Who complied with the vaccination schedule.
- Who did not receive a concomitant medication/ product/vaccine leading to the elimination from the ATP analysis up the one month post-Dose 2 visit (Visit 6, Day 90).

Statistical Analysis Plan

Study alias & e-track number(s): NTHI MCAT-001 (201281)

- Who did not present with an intercurrent medical condition leading to elimination from the ATP analysis up to the one month post-Dose 2 visit (Visit 6, Day 90).
- Who complied with the immunogenicity blood sample timings at 1 month post-Dose 2 visit (Visit 6, Day 90).
- For whom post-Dose 2 immunogenicity results are available for at least one assay.

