6.1.2.2. According-to-protocol cohort for analysis of persistence of immunogenicity (Epoch 002)

The ATP cohort for persistence of immunogenicity will include all evaluable subjects, i.e., those who were included in the ATP cohort for immunogenicity, or were excluded from this cohort solely because they had no blood samples taken or because of non-compliance with blood sample timings up to the one month post-Dose 2 visit (Visit 6, Day 90), and:

- Who did not receive a concomitant medication/ product/vaccine leading to elimination from the ATP analysis for immunogenicity.
- Who did not present with an intercurrent medical condition leading to elimination from the ATP analysis for immunogenicity.
- Who complied with at least one of the blood sample timings after the one month post-last vaccination visit (Visit 6, Day 90).
- For whom persistence immunogenicity results are available for at least one assay in at least one of the two persistence time points (Visit 7, Day 210 and Visit 8, Day 420).

The list of applicable elimination codes for each cohort can be found in the study specific form FORM-BIO-CLIN-9004-05 Criteria for eliminating subjects from the analyses.

Cohort	Elimination codes	Eli Type
ATP cohort for analysis of immunogenicity	1010-2500	MA
ATP cohort for analysis of persistence of immunogenicity	1010-2500	FU

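### SAP 7.2.3 and protocol 10.6.3 name the Epoch 001 ATP cohort for the immunogenicity analysis up to Day 420, and no analysis paragraph names the persistence cohort defined for Epoch 002

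*SAP*

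**What the plan says.** SAP section 6.1.2 says that the ATP cohorts are defined by epoch, and two are then set out.

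- **Epoch 001 (6.1.2.1, elimination type MA).** The definition opens "The ATP cohort for immunogenicity will include all subjects in the TVC". Two of its conditions are "Who complied with the immunogenicity blood sample timings at 1 month post-Dose 2 visit (Visit 6, Day 90") and "For whom post-Dose 2 immunogenicity results are available for at least one assay". Its conditions on concomitant products and intercurrent conditions run only up to Visit 6 (Day 90).
- **Epoch 002 (6.1.2.2, elimination type FU).** The definition opens "The ATP cohort for persistence of immunogenicity will include all evaluable subjects, i.e., those who were included in the ATP cohort for immunogenicity". It also admits those "excluded from this cohort solely because they had no blood samples taken or because of non-compliance with blood sample timings" up to Day 90. It adds the condition "Who complied with at least one of the blood sample timings after the one month post-last vaccination visit (Visit 6, Day 90") and requires a persistence result at Day 210 or Day 420. Its product and condition eliminations carry no Day 90 limit.

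Section 7.2.3, which governs the analysis up to Day 420, then states: "The primary analysis will be performed on the ATP cohort for immunogenicity and if, in any study group". The rest of that sentence adds a second analysis on the TVC if at least 10% of vaccinated subjects with serological results in any group are excluded. Section 7.1.3 (up to Day 90) and protocol 10.6.3 contain the same sentence. Sections 7.2.3.1 and 7.2.3.2 apply it to every humoral and CMI sampling time point, so Day 210 and Day 420 fall under it.

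**The concern.** The definitions and the analysis section do not agree. The plan builds a cohort for the persistence time points, then assigns the analysis containing those time points to the other cohort. Taken as written, this has two consequences at Day 210 and Day 420.

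1. A subject who, after Day 90, receives a product or develops a condition listed as a possible ground for elimination (protocol 6.6.2 and 6.7: for example immunoglobulins, blood products, chronic immunosuppressants, an immune-altering condition) stays in the primary persistence summaries.
2. A subject whose only fault is a missing or mistimed sample at Day 90 is left out, even with valid later samples.

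Persistence of the humoral and CMI response at these two visits is a named secondary endpoint. The statistician is unblinded at the Day 90 analysis (SAP 9.1), so the population for the later time points should be settled in writing and not inferred afterwards.

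**Working it through.** The plan states no figure to reproduce here. The check is a comparison of texts, followed by three small calculations.

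**1. The two cohorts against the rule applied**

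| Condition | Epoch 001 cohort (6.1.2.1) | Persistence cohort (6.1.2.2) |
|---|---|---|
| Eliminating product or condition | Counts only up to Day 90 | No Day 90 limit |
| On-time Day 90 sample | Required | Failure on this alone is forgiven |
| Result needed | Post-Dose 2, at least one assay | Day 210 or Day 420, at least one assay |
| On-time sample after Day 90 | Not required | At least one |
| Named in SAP 7.2.3 | Yes | No |

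The persistence cohort appears in its definition and in the elimination-code table. No paragraph of SAP section 7 or protocol 10.6 names it. Under the Epoch 001 rule, eliminations stop for 420 - 90 = 330 of the 420 days.

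**2. What the TVC analysis can repair**

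Inputs: about 30 per Step 2 group and 15 per Step 1 group (protocol 4.1 and 10.3), or 15 + 30 = 45 if placebo is pooled as in SAP 7.2. The trigger is the smallest k with k/n of at least 10%.

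- n=30: k=3 (10.0%), so up to 2 (6.7%) can be left out with no second analysis.
- n=15: k=2 (13.3%), so up to 1 (6.7%).
- n=45: k=5 (11.1%), so up to 4 (8.9%).

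In total, 2×1 + 3×2 = 8 of 120 subjects can be left out without a trigger over five groups, or 1 + 2×2 + 4 = 9 of 120 with pooled placebo.

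The documents give no exclusion rate. Assume independent exclusion with probability q and full groups, and let F_n be the binomial probability of staying below the trigger in a group of n. The chance that no group triggers is F_15² × F_30³ for five groups, or F_15 × F_30² × F_45 with pooled placebo.

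| q (assumed) | Expected excluded per 30 | No trigger, five groups | No trigger, pooled placebo |
|---|---|---|---|
| 2% | 0.6 | 87% | 92% |
| 5% | 1.5 | 37% | 51% |
| 10% | 3.0 | 2% | 5% |

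Here q covers exclusion for any reason, because the trigger does not separate reasons.

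The TVC analysis does nothing for the subjects in consequence 1. They do not count as excluded, and the TVC contains all vaccinated subjects with data.

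**3. Effect of one subject on a GMC**

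A GMC is 10 to the power of the mean log10 concentration. Shifting one of n subjects by a factor f multiplies it by f^(1/n). The 10-fold shift is an assumption with no source in the documents, shown in both directions.

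- n=30: 10^(1/30) = 1.08 and 10^(-1/30) = 0.93, so +8%/-7%.
- n=15: 10^(1/15) = 1.17 and 10^(-1/15) = 0.86, so +17%/-14%.
- n=45: 10^(1/45) = 1.05 and 10^(-1/45) = 0.95, so +5%/-5%.

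One subject is 1/30 = 3.3%, 1/15 = 6.7% or 1/45 = 2.2% of the group. The CMI sub-cohort has about 15 per Step 2 group (protocol 4.1), so one subject is 6.7% there.

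**The case against.** A reader might infer that the persistence cohort will never be used. The documents do not show that. The cohort is headed Epoch 002, the SAP says that ATP cohorts are defined by epoch and will be evaluated, and its abbreviation list ties type FU to the follow-up analysis and MA to the main analysis. The table annex (TFL) and the elimination-criteria form are not among the documents seen, and either could name the cohort. This stands as evidence of intent, and limits the claim to what the SAP and protocol text say.

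The label could also be shorthand for the ATP cohort of the relevant epoch. Protocol 6.7 uses it for conditions arising at any time during the study. Against this, SAP 6.1.2.2 uses the same label for the other cohort, when it describes subjects included in it or "excluded from this cohort solely because they had no blood samples taken or because of non-compliance with blood sample timings". Within the SAP it is therefore a specific name, and 7.2.3 points to the Epoch 001 definition.

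A reader might also infer that Day 90 compliance alone decides who counts later, or that valid late samples are lost outright. Neither holds. The other ATP conditions also apply, and the TVC analysis brings back all vaccinated subjects with data once a group reaches 10%. That limits the second consequence but not the first.

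Finally, the sentence in 7.2.3 is right for part of its section. The one-month post-Dose 2 ANCOVA and the summary score are repeated there and properly use the Epoch 001 cohort.

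**Conclusion.** The stated rule for Day 210 and Day 420 is wrong as written and should be corrected. It is most likely a carried-over sentence and not a deliberate choice.

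Its reach is narrow. It touches the descriptive humoral and CMI summaries at two visits, which are secondary endpoints. No power or type I error statement depends on them. It would be tempting to infer that formulation selection is biased. The documents do not support that, because the ANCOVA and the summary score use results one month after Dose 2.

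The number of subjects affected in either direction cannot be derived from the documents. The GMC shifts above are illustrations for one subject, and the trigger probabilities assume independent exclusion and full groups. Two statements need no such assumption: under the literal rule no planned analysis removes interference after Day 90, and the TVC analysis addresses the omitted subjects only from 10% exclusion upward.

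**What to change.** Add to SAP 7.2.3, and mirror in protocol 10.6.3, a sentence stating that:

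- Day 210 and Day 420 humoral and CMI results use the ATP cohort for persistence of immunogenicity (type FU);
- Day 0 to Day 90 results, the Day 90 ANCOVA and the summary score keep the Epoch 001 ATP cohort (type MA);
- the 10% trigger for the TVC analysis applies to each cohort separately.

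The cost is one sentence in each document. Both cohort definitions and the elimination codes already exist, and no sample size or power figure changes. The net change in the number analysed at Day 210 and Day 420 cannot be computed in advance, because some subjects would be re-admitted and others removed.
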